7.2 General Study Procedures

A signed and dated IRB/IEC-approved informed consent must be obtained before any study-specific procedures are performed.

Procedures that are part of routine care are not considered study-specific procedures and may be used at screening to determine eligibility. All subjects will be screened for eligibility before enrollment. Only eligible subjects will be enrolled into the study. During treatment, assessments and procedures can be performed within 3 days of the planned visit. It is recommended that dosing occur on the same day of the week (eg, if first dose is administered on Monday, all subsequent doses should be administered on a Monday), however a \pm 3-day dosing and study procedure window is allowed.

The following laboratory analytes in [Table 6](#) will be assessed at various times throughout the study.

Table 6. Laboratory Analytes

Chemistry	Coagulation	Endocrine Function	Hematology	Other Labs
Sodium	PT or INR	TSH	RBC	Urine or serum pregnancy test
Potassium	PTT or aPTT	T3 (or FT3 per local standard)	Hemoglobin	Urinalysis
Chloride		FT4	Hematocrit	Specific gravity
Bicarbonate or CO2		Cortisol	MCV	pH
Total protein			MCH	Blood
Albumin			MCHC	Protein
Calcium			RDW	Glucose
Magnesium			Reticulocytes	Bilirubin
Phosphorus			Platelets	Microscopic exam (performed at the discretion of the Principal Investigator)
Glucose			WBC	Hep B surface antigen and Hep B total core antibody
BUN or Urea			Differential	Hep C antibody
Creatinine			• Total Neutrophils or Bands/stabs and Segmented Neutrophils [^]	HIV
Uric acid			• Eosinophils [^]	CA 19-9 and CEA
Total bilirubin			• Basophils [^]	Tumor PD-L1 testing
Direct bilirubin			• Lymphocytes	Anti-AMG 820 antibody
Alkaline phosphatase			• Monocytes or Mid Cell Fraction	AMG 820 PK
AST (SGOT)			Nucleated RBC	Anti-pembrolizumab antibody
ALT (SGPT)				Pembrolizumab PK
Amylase				Biomarkers development and immunophenotyping blood
Lipase				Archived tumor tissue
				Fresh tumor biopsy tissue
				Serum IL34, IL10, VEGF, MCP-1, MMPs, CSF-1

[^]Local lab may report Granulocytes instead of Neutrophils, Eosinophils, and Basophils individually
 AST = aspartate aminotransferase; ALT = alanine aminotransferase ; PT = prothrombin time;
 INR = international normalization ratio; PTT/aPTT = partial thromboplastin time/activated partial thromboplastin time; TSH = thyroid stimulating hormone; T3/FT3=free triiodothyronine ; FT4 = free thyroxine; PD-L1 = programmed cell death-1 ligand 1.

7.2.1 Screening Enrollment

The following procedures are to be completed during the screening period within 28 days of enrollment at time points designated in the Schedule of Assessments (Table 5):

- Confirmation that the Informed Consent Form has been signed.
- Demographic data including sex, age, race, and ethnicity will be collected in order to study their possible association with subject safety and treatment effectiveness. Additionally demographic data may be used to study the impact on biomarkers variability and pharmacokinetics of the protocol required therapies.
- Vital signs (systolic/diastolic blood pressure, heart rate, respiratory rate, temperature): Subject should be in a supine position in a rested and calm state for at least 5 minutes before blood pressure assessments are conducted. If the subject is unable to be in the supine position, the subject should be in most recumbent position as possible. The position selected and temperature location for a subject should be the same that is used throughout the study and documented on the vital sign CRF. Record all measurements on the vital signs CRF.
- Complete medical and surgical history will be collected. Medical history will include information on the subject's concurrent medical conditions. The current toxicity grade will be collected for each condition that has not resolved. Disease history must date back to the original diagnosis. Record all findings on the medical history CRF.
- Medication History: Therapy name, indication, dose, unit, frequency, and start and stop date will be collected for prior therapies taken for current or prior malignancies.
- Physical examination as per standard of care including ECOG performance status assessment. Physical examination findings should be recorded on the appropriate CRF (eg, medical history, event).
- Body weight in kilograms should be measured without shoes.
- Height in centimeters should be measured without shoes.
- Documentation of concomitant medications (per Section 6.5).
- A 12-lead electrocardiogram (ECG) per standard of care: The ECG must include the following measurements: heart rate, PR interval, QRS, QT and QTc intervals. Subject must be in supine position in a rested and calm state for at least 5 minutes before ECG assessment is conducted. If the subject is unable to be in the supine position, the subject should be in most recumbent position as possible. The investigator or designated site physician will review all ECGs. Once signed, the original ECG tracing will be retained with the subject's source documents. At the request of the sponsor, a copy of the original ECG will be made available to the Sponsor.
- Local Laboratory Assessments:
 - Within \leq 28 days prior to enrollment:
 - hematology panel
 - chemistry panel
 - lipase and amylase
 - hepatitis B surface antigen and Hepatitis B core antibody

- hepatitis C virus antibody
- HIV
- coagulation: PT or INR and PTT or aPTT
- thyroid function tests: T3 (or FT3), FT4, TSH
- urinalysis
- Serum or urine pregnancy test for female subjects of childbearing potential
- Central Laboratory Assessment
 - Obtaining of tumor tissue for biomarker analyses is required as described below:
 - Submit a newly obtained or recent (tissue obtained within 3 months prior to day 1 and no systemic therapy given since the biopsy) formalin-fixed paraffin-embedded tumor biopsy tissue and associated pathology report from the primary or metastatic lesion for PD-L1 analysis and for biomarker analysis within 28 days prior to enrollment. Subjects with an inadequate or indeterminate samples may undergo re-biopsy, when feasible, as per the investigator assessment. PD-L1 testing will be performed at central laboratory. This tumor biopsy is required:
 - in all NSCLC subjects naïve to PD-1/PD-L1 inhibitors
 - whenever feasible in NSCLC subjects refractory/relapsing during treatment with PD-1/PD-L1 inhibitors, if enrolling immediately after into the current study and upon discussion with the Sponsor
 - in all CRC subjects
 - Whenever feasible in pancreatic cancer subjects
 - If available, submit also a formalin fixed paraffin embedded archival tumor tissue sample and associated pathology report.
- Radiographic tumor imaging assessment must include CT or MRI scans of the chest, abdomen and pelvis. MRI of the brain should be performed for all NSCLC subjects at screening, and in any subject if clinically indicated. See [Section 7.4](#).
- Recording of serious adverse events that occur after subject signs informed consent
- Review of inclusion and exclusion criteria

Subjects may be rescreened. If a subject is being rescreened, he or she may need to re-consent to the study to ensure that the IRB/IEC approved main informed consent form is signed within 28 days of enrollment or randomization.

7.2.2 Treatment

Treatment begins when the first dose of protocol-required therapies is administered to a subject.

The following procedures will be completed during the treatment period at the times designated in the Schedule of Assessments ([Table 5](#)). Administration of

protocol-required therapies is to be performed after all other procedures are completed during each visit that it is required, unless otherwise stated.

- Physical examination as per standard of care including ECOG performance status assessment. Physical examination findings should be recorded on the appropriate CRF (eg, medical history, adverse event)
- Vital signs (systolic/diastolic blood pressure, heart rate, respiratory rate, temperature): Subject should be in a supine position in a rested and calm state for at least 5 minutes before blood pressure assessments are conducted. If the subject is unable to be in the supine position, the subject should be in most recumbent position possible. The blood pressure position selected and temperature location for a subject should be the same that is used throughout the study and be documented on the vital signs CRF.
- Local laboratory assessments: On treatment tests can be performed within 2 days of the planned visit. Results should be reviewed prior to the administration of study treatment:
 - hematology panel
 - chemistry panel
 - lipase and amylase
 - coagulation: PT or INR and PTT or a PTT
 - thyroid function tests: T3 (or FT3), FT4, TSH
 - urinalysis
 - Serum or urine pregnancy test for female subjects of childbearing potential: Additional, on-treatment pregnancy testing may be performed at the investigator's discretion.
- Central laboratory assessments (refer to Schedule of Assessments as not all tests will be required after Amendment 2):
 - whole blood for biomarker analyses (Immunophenotyping)
 - serum for biomarker analyses of baseline circulating markers (IL34, IL10, VEGF MCP-1, MMPs, CSF-1)
 - Blood for immunogenicity (anti-AMG 820 antibody and anti-pembrolizumab antibody). Note: All samples should be drawn within 24 hours before infusion of AMG 820 or pembrolizumab and at the same time as the pre-dose trough blood collection for the PK sample.
 - blood for PK of AMG 820 and pembrolizumab
 - biomarker development blood sample
 - tumor tissue biopsy for biomarker analyses is strongly encouraged in all subjects
 - Recommended collection of biopsies during the study at the time of the second CT scan at week 10 ± 2 weeks (formalin-fixed paraffin-embedded tumor biopsy tissue and associated pathology report, if available) or whenever feasible. Subjects with an inadequate or indeterminate samples may undergo re-biopsy, when feasible, as per the investigator assessment.

- Radiographic tumor imaging assessments must include CT scan or MRI scans of the chest, abdomen and pelvis. In addition, MRI of the brain will be performed if signs or symptoms suggestive of CNS metastasis are present. Imaging will be performed per the Schedule of Assessment ([Table 5](#)).
- AMG 820 administration. Note: AMG 820 must be administered before pembrolizumab
- Pembrolizumab administration
- Recording of adverse events, serious adverse events and disease related events
- Documentation of concomitant medications (see [Section 6.5](#))

7.2.3 Safety Follow-up Visit(s)

All subjects will complete a safety follow-up visit approximately 135 (+7) days after the last dose of study treatment.

The following procedures will be performed:

- Physical examination as per standard of care including ECOG performance status assessment. Physical examination findings should be recorded on the appropriate CRF (eg, medical history, event)
- Body weight in kilograms should be measured without shoes.
- Vital signs (systolic/diastolic blood pressure, heart rate, respiratory rate, temperature): Subject should be in a supine position in a rested and calm state for at least 5 minutes before blood pressure assessments are conducted. If the subject is unable to be in the supine position, the subject should be in most recumbent position as possible. The position selected and temperature location for a subject should be the same that is used throughout the study and documented on the vital sign CRF. Record all measurements on the vital signs CRF
- A 12-lead ECG per standard of care: The ECG must include the following measurements: heart rate, PR, QRS, QT and QTc intervals. Subject must be in supine position in a rested and calm state for at least 5 minutes before ECG assessment is conducted. If the subject is unable to be in the supine position, the subject should be in most recumbent position as possible. The investigator or designated site physician will review all ECGs. Once signed, the original ECG tracing will be retained with the subject's source documents. At the request of the sponsor, a copy of the original ECG will be made available to the Sponsor.
- Local laboratory Assessments
 - hematology panel
 - chemistry panel
 - lipase and amylase
 - coagulation: PT or INR and PTT or a PTT
 - thyroid function tests: T3 (or FT3), FT4, TSH
 - urinalysis
 - serum or urine pregnancy test for female subjects of childbearing potential

- Central laboratory assessments (refer to Schedule of Assessments as not all tests will be required after Amendment 2):
 - All subjects
 - Blood for immunogenicity
- Radiographic tumor imaging and tumor response assessments are to be performed if the subject ended study treatment prior to confirmed PD per irRECIST and has not had assessments performed within 6 weeks of the visit.
 - Radiographic tumor imaging assessments must include CT scan or MRI scans of the chest, abdomen and pelvis. In addition MRI of the brain will be performed if signs or symptoms suggestive of CNS metastasis are present.
- Recording of adverse events
- Recording of serious adverse events. Note: Serious adverse events that occur through 135 (+7) days after the cessation of all study treatment are recorded in the subject's medical record and are submitted to Amgen.
- Recording of disease related events
- Documentation of concomitant medications (see [Section 6.5](#))

7.2.4 Long-term Follow-up

After the safety follow-up visit all subjects will enter the long-term follow-up. Subjects will be contacted by clinic visit or telephone to assess survival, disease status and initiation of first subsequent anti-tumor therapy following end of AMG 820 and pembrolizumab treatment.

Contact for all subjects will be attempted every 12 weeks (\pm 28 days) following the safety follow-up visit, as applicable, until death, subject withdraws full consent, or up to 12 months after subject's enrollment for the study, whichever comes first.

For subjects who discontinued treatment for any reason other than confirmed PD, every effort should be made to perform radiographic imaging (CT or MRI) of the chest, abdomen and pelvis, along with tumor assessments of all other sites of disease every 12 weeks until documentation of confirmed PD per irRECIST, clinical progression, start of new anticancer therapy, or up to 12 months after subject's enrollment for the study, whichever occurs first.

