^j Radiographic imaging (CT or MRI) of the chest, abdomen and pelvis, and MRI of the brain if a subject has signs and symptoms suggestive of CNS metastases, are required at screening. MRI of the brain is required for all NSCLC subjects at screening. Tumor assessments must also include all other sites of disease. The screening scans must be done within 28 days prior to enrollment. During treatment, radiographic imaging (CT or MRI) of the chest, abdomen and pelvis, along with tumor assessments of all other sites of disease, (MRI of the brain if a subject has symptoms or signs suggestive of CNS metastases), will be performed independent of treatment cycle at week 10 (± 1 week), and then every 10 weeks (± 2 weeks) or more frequently if clinically indicated until confirmed PD per irRECIST or start of new anticancer treatment. Imaging should not be adjusted for cycle initiation delays and performed according to the calendar. The imaging modality selected (eg, CT or MRI) should remain constant for any individual subject. Response or progression should be confirmed by repeated radiographic imaging ≥ 4 weeks after the first indication of response or progression. Radiographic imaging is required at the safety follow-up visit if the subject ended treatment prior to confirmed PD and has not had radiographic tumor imaging performed within 6 weeks (+1 week) of the visit. The radiographic images will be submitted to a central imaging lab.

^k PK samples should be collected at the exact nominal time point as noted, where collection times are to be defined relative to the end of AMG 820 infusion. If unable to collect a PK sample at the specified nominal time point collect it as close as possible to the nominal time point and record the actual collection time. PK samples not collected at exact nominal time point will not be considered protocol deviations.

^m Safety labs should be performed and reviewed within 2 days prior to each dose.

ⁿ CEA for CRC and CA 19-9 for pancreatic cancer every 6 weeks ± 2 weeks

^o For subjects who discontinued treatment for any reason other than confirmed PD, every effort should be made to perform radiographic imaging (CT or MRI) of the chest, abdomen and pelvis, along with tumor assessments of all other sites of disease every 12 weeks until documentation of confirmed PD per irRECIST, clinical progression, start of new anticancer therapy, or up to 12 months after subject's enrollment for the study, whichever occurs first.

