 - irPD – increases in number or size of non-index lesion(s) does not constitute progressive disease. New lesions that are measurable up to 5 new lesions per organ and 10 total) are included in the calculation of tumor burden in response assessments
- Overall response
 - irCR – complete disappearance of all lesions (whether measurable or not, and no new lesions)
 - Confirmation by a repeat, consecutive assessment no less than 4 weeks from the date of the first documented response
 - irPR – decrease in tumor burden \geq 30% relative to baseline.
 - Confirmation by a repeat, consecutive assessment no less than 4 weeks after the first documentation
 - irSD – not meeting criteria for irCR or irPR, in the absence of irPD
 - irPD – increase in tumor burden \geq 20% relative to nadir (minimum recorded tumor burden) and at least 5 mm absolute increase compared to nadir.
 - Confirmation by a repeat, consecutive assessment no less than 4 weeks from the date of the first documented assessment.

Response confirmation:

- irCR and irPR:
 - the repeat confirmation scan may be performed any time after 4 weeks from the first suspected radiologic evidence of response and may be delayed until the next scheduled scan to avoid necessary procedures
- irPD:
 - In subjects who have initial evidence of radiological PD by irRECIST (irPD on one scan), it is at the discretion of the PI whether to continue a subject on study treatment until repeat imaging is obtained based on their assessment of clinical stability. Subjects may receive study treatment and tumor assessment should be repeated ≥ 4 weeks later in order to confirm irPD per site assessment.
 - In determining whether or not the tumor burden has increased or decreased per irRECIST, the local site investigator should consider all index as well as any incremental new measureable lesion(s).
 - irPD is confirmed at repeat imaging (irPD on two consecutive scans at least 4 weeks apart) if tumor burden remains $\geq 20\%$ and at least 5 mm absolute increase compared to nadir

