 - Subjects with a global deterioration of health status requiring discontinuation of treatment without radiographic confirmation of disease progression (confirmed irPD) at the time should have the reason for treatment discontinuation classified as 'clinical disease progression'. In this case, irPD cannot be assigned at the time as the overall objective tumor response. Every effort should be made to radiographically confirm irPD even after discontinuation of treatment.

Measurement and Tumor Response Assessment Based on modified irRECIST	
Measurable lesions	
 • ≥ 10 mm (unidirectional measure) • Pathologic lymph nodes: short axis ≥ 15 mm
Measurement of each lesion	The longest diameter (mm)
The sum of the measurements (SLD)	
 • The sum of the longest diameters (SLD) of all index lesions and new measurable lesions, if any • Up to 5 lesions per organ, up to 10 total
Response assessment	
 • irPD: $\geq 20\%$ increase from nadir and at least 5 mm absolute increase compared to nadir (requires confirmation) • irSD: $< 30\%$ decrease from baseline and $< 20\%$ increase from nadir • irPR: $\geq 30\%$ decrease from baseline (requires confirmation) • irCR: Disappearance of all lesions (requires confirmation)
New Lesions	The presence of new lesion(s) does not define progression. Measurable new lesions (≥ 10 mm): The measurements of the new lesions(s) are included in the SLD
Confirmation	Confirmation by 2 consecutive observations at least 4 weeks apart required for irCR, irPR and irPD.

Modified irRECIST Overall Response Assessment			
Measurable Response	Non-measurable Response		Overall Response
Index and new measurable lesions (tumor burden) ^a , %	Non-Index lesions	New non-measurable lesions	Using irRECIST
↓ 100%	Absent	Absent	irCR ^b
↓ 100%	Stable/NA	Any	irPR ^b
↓ 100%	Unequivocal progression	Any	irPR ^b
↓ $\geq 30\%$	Absent/Stable/NA	Any	irPR ^b
↓ $\geq 30\%$	Unequivocal progression	Any	irPR ^b
↓ $< 30\%$ to ↑ $< 20\%$	Absent/Stable/NA	Any	irSD
↓ $< 30\%$ to ↑ $< 20\%$	Unequivocal progression	Any	irSD
↑ $\geq 20\%$	Any	Any	irPD ^b
UE	Any	Any	UE
ND	Any	Any	UE
NA	Any	Any	UE

NA = not available; ND = not done; UE = unable to evaluate

^a Decrease assessed relative to baseline, including new measurable lesions (≥ 10 mm)

^b Response (irCR, irPR) and progression (irPD) are confirmed by a second, consecutive assessment at least 4 weeks apart.

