#### Investigational Product

The term 'investigational product' is used in to reference to AMG 820 in combination with pembrolizumab.

---

Last Investigational Product Dose Date

The last AMG 820 dose date for each subject is defined as the latest date AMG 820 is administered.

Objective Response as per irRECIST (irOR)

Objective response is defined as a complete response or partial response, as defined by the irRECIST. Confirmation is done by a repeat, consecutive assessment no less than 4 weeks from the date of first documented assessment.

Objective Response Rate as per irRECIST (irORR)

Immune-related ORR (irORR) is defined as the percentage of subjects with irOR.

Overall Survival Time

Overall survival time is calculated as the number of days from the first administration of AMG 820 to death or if applicable censoring [(date of death or censoring – date of first dose of AMG 820 + 1)]. Subjects who withdraw from treatment without withdrawing consent will be followed for survival status up to 12 months.

Subjects who are alive (no record of death) and are lost to follow-up will be censored at the date of last contact.

Progression-Free Survival Time per irRECIST (PFS)

Progression-free survival time is calculated as the number of days from the first administration of AMG 820 to the first assessment of disease progression as per irRECIST or death due to any cause, or if applicable date of censoring (date of progressive disease or death or censoring – first administration of AMG 820 +1).

The following censoring strategies will be used for the progression free survival analysis:

If a subject's disease has not progressed and the subject is alive, progression-free survival time will be censored at the last date they are known to be progression-free (ie, the last evaluable radiological assessment date).

If a subject has no tumor evaluation in the study, progression-free survival time will be censored at the date of the first administration of AMG 820.

Subjects who withdraw consent to participate in the study prior to disease progression will be censored at their last evaluable radiological assessment date.

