### Time to progression per irRECIST (TTP)

Time to progression is calculated as the number of days from the first administration of AMG 820 to the first objective assessment of disease progression as per irRECIST, clinical progression, or if applicable date of censoring (date of progressive disease or censoring – date of first administration of AMG 820 +1). The following censoring strategies will be used:

If a subject's disease has not progressed, time to progression will be censored at the last date they are known to be progression-free (ie, the last evaluable radiological assessment date).

If a subject has no tumor evaluation in the study, time to progression will be censored at the date of the first administration of AMG 820.

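### Off-treatment imaging stops at clinical progression in Protocol 7.2.4 and Table 5 footnote o, but Appendix D asks for irPD still to be confirmed by imaging; PFS and DOR can be modestly overstated

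*Protocol*

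**What the plan says.** - **Imaging stop rule.** Protocol 7.2.4 applies to subjects who stopped treatment for any reason other than confirmed PD. It asks for imaging "every 12 weeks until documentation of confirmed PD per irRECIST, clinical progression, start of new anticancer therapy" or 12 months from enrollment, whichever is first. Table 5 footnote o has the same list: "until documentation of confirmed PD per irRECIST, clinical progression, start of new anticancer therapy".
- **Appendix D (response confirmation, irPD).** A subject who stops for global deterioration without confirmed irPD is recorded as clinical disease progression. For that subject "irPD cannot be assigned at the time as the overall objective tumor response", and "Every effort should be made to radiographically confirm irPD even after discontinuation of treatment".
- **SAP section 6, PFS.** Time runs "to the first assessment of disease progression as per irRECIST or death due to any cause". If the subject is alive without such progression, "progression-free survival time will be censored at the last date they are known to be progression-free", meaning the last evaluable scan. DOR likewise ends at irRECIST progression or death.
- **SAP section 6, TTP.** Time runs "to the first objective assessment of disease progression as per irRECIST, clinical progression, or if applicable date of censoring". Clinical progression is an event here but not in PFS.
- **Other scans that remain.** Protocol 7.4 calls for a scan at end of treatment (EOT) if the last one was at least 6 weeks earlier and PD is not confirmed. Section 7.2.3 calls for one at the safety visit, 135 (+7) days after the last dose, if PD is not confirmed and there has been no assessment within 6 weeks. For irPD, Appendix D requires "Confirmation by a repeat, consecutive assessment no less than 4 weeks from the date of the first documented assessment"; Table 5 footnote j and section 7.4 say the same in substance. Section 7.4 dates PD at its first observation.

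**The concern.** Appendix D asks for scans in the very subjects whose status ends the scan series in 7.2.4 and footnote o. The on-treatment rule in 7.4 and footnote j stops only at confirmed PD or new anticancer treatment, so clinical progression as a stop is peculiar to the off-treatment series.

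This matters because PFS and DOR depend on imaging. A subject who has clinically progressed becomes an event only through irRECIST progression or death. If 7.2.4 is followed, that subject may be dated late at the safety visit, dated at death, or censored at a scan taken before the deterioration. Whether a subject leaves the imaging series then depends on outcome, and each route lengthens recorded PFS. Because TTP counts clinical progression, the same subject can have a TTP shorter than PFS, the reverse of what the two definitions should allow. The SAP has no rule or sensitivity analysis for this case.

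**Working it through.** The plan states no figure on this point, so there is none to reproduce.

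**1. The gap, from the protocol's own windows.** Take a subject whose last scan was just under 42 days before EOT, so that no EOT scan is required. The next required scan is at the safety visit.

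- If EOT is the day of the last dose: 42 + 135 = 177 to 42 + 142 = 184 days since the last scan.
- If EOT is 21 days after the last dose: 42 − 21 + 135 = 156 to 42 − 21 + 142 = 163 days.
- Delay from EOT to that scan: 135-142 days in the first case, 114-121 days in the second.
- The on-treatment interval is 10 weeks, or 70 days.

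**2. When the 12-weekly series starts.** Section 7.2.4 opens with the period after the safety visit. If the 12 weeks run from there, the first scan is due about 135 + 84 = 219 days after the last dose. If they run from treatment stop, it is due at 84 days. The text does not say which.

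**3. Size, under assumptions.** The documents give none of these rates:

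- 10% or 30% of progressions are clinical only
- exponential time to progression, median 2.5 or 4 months
- exponential survival after progression, median 3 or 6 months
- on-treatment scans every 70 days; follow-up to 12 months
- EOT and last dose on the day of clinical progression; an EOT scan if the last scan was at least 42 days earlier, counted as irPD on that day

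Kaplan-Meier PFS at 6 months (183 days) was simulated with 300,000 subjects per setting. In A, scans run 12-weekly from treatment stop. In B, the next scan after any EOT scan is at day 135, and it counts. In C, no scan after EOT establishes irPD: only death counts, otherwise the subject is censored at the last scan before deterioration.

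| Clinical only | Median progression / later survival (months) | A | B | C | B − A | C − A |
|---|---|---|---|---|---|---|
| 10% | 2.5 / 3 | 26.7% | 27.3% | 27.9% | 0.6 | 1.3 |
| 10% | 2.5 / 6 | 27.4% | 28.3% | 29.1% | 0.9 | 1.7 |
| 10% | 4 / 3 | 43.7% | 44.2% | 44.7% | 0.5 | 0.9 |
| 10% | 4 / 6 | 44.5% | 45.2% | 45.9% | 0.7 | 1.4 |
| 30% | 2.5 / 3 | 27.1% | 28.9% | 30.8% | 1.8 | 3.7 |
| 30% | 2.5 / 6 | 28.0% | 30.6% | 33.1% | 2.6 | 5.1 |
| 30% | 4 / 3 | 44.1% | 45.6% | 47.0% | 1.5 | 2.9 |
| 30% | 4 / 6 | 45.0% | 47.2% | 49.2% | 2.2 | 4.2 |

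Differences are taken before rounding. About one third of clinical-only subjects (32-36%) qualify for the EOT scan; the rest do not.

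Varying the conventions (EOT a week after deterioration, last dose up to 21 days before EOT, survival required to a confirming scan) moves C − A to 0.8-2.1 points at 10% and 2.3-6.3 at 30%. It moves B − A to 0.4-1.3 and 1.1-3.8.

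**4. Comparison with sampling error.** √(p(1 − p)/n) at n = 29 is √(0.27 × 0.73/29) = 8.2 points for PFS of 27%, and √(0.45 × 0.55/29) = 9.2 points for 45%.

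**The case against.** **A reader might infer that no confirming scan is available after EOT or the safety visit.** The documents do not support that. Footnote j, section 7.4 and Appendix D call for a repeat scan at least 4 weeks after any first irPD, and do not limit this to subjects on treatment. An irPD first seen at EOT can be confirmed at the safety visit and keeps its EOT date. What remains is the subject who qualifies for no EOT scan.

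**A reader might also infer a bias of 6-10 points.** That size arises if the EOT scan is left out and the comparison is with a scan within one month of clinical progression, which neither the protocol nor a wording change would supply.

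**The passages can be read together.** Section 7.2.4 covers everyone who stopped without confirmed PD, so clinical progression on its list could mean an event arising later in follow-up. Neither passage forbids extra scans. This is a possible reading, but the text does not state it, and a site that stops at clinical progression is following 7.2.4 as written. Different practice between sites is therefore a risk, not something the documents show.

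**Unconfirmed irPD may count in PFS.** The SAP refers to the first assessment of progression and sets out a confirmation rule only under objective response. If a single safety-visit scan counts, column B applies and the effect is about half of column C.

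**These progressions are captured in TTP, and the affected endpoints are secondary and descriptive.** Both statements are correct. They limit the consequence but leave PFS and DOR with the bias.

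**Conclusion.** The contradiction is in the current text and its effect on PFS follows from the SAP's event and censoring rules. Under the stated assumptions, 6-month PFS is overstated by about 1-2 points if 10% of progressions are clinical only and 3-5 points if 30% are, where no scan after EOT establishes irPD. It is about half that where the safety-visit scan counts. The comparator is 12-weekly imaging from treatment stop, with the EOT scan allowed for.

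The bias is smaller than the standard error at n = 29, but it runs in one direction and more subjects would not remove it. The direction is the same for DOR, which concerns responders only; its size was not calculated.

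A reader might take this as weakening the trial's main conclusion. It does not: ORR is the primary efficacy endpoint, the Simon decisions rest on it, and neither uses the off-treatment progression date. The point is worth correcting, at moderate priority.

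**What to change.** 1. **Protocol 7.2.4 and Table 5 footnote o:** reconcile with Appendix D by removing clinical progression from the list of reasons to end imaging. Keep the existing best-effort basis, for subjects able to attend.
2. **Same passages:** state that the 12-week interval runs from end of treatment. If it is left to run from the safety visit, removing the stop reason recovers little.
3. **CRF:** record the date of clinical progression separately.
4. **SAP section 6 and 10.6.2:** state how clinical progression without irPD is handled in PFS and DOR, and whether an unconfirmed irPD counts. Add a sensitivity analysis of both endpoints with clinical progression as an event on its recorded date.

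The cost is wording in two protocol passages, one date field and one extra analysis. There would be a few more follow-up scans, which Appendix D already requests. Item 4 needs no new imaging; with the date from item 3, it is useful even where subjects are too ill to be scanned.
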